3.4 Additional Efficacy Endpoints

All variables listed as primary or secondary endpoints will be analyzed at all applicable visits other than those listed above. In addition, the following endpoints will be evaluated at all applicable visits unless otherwise specified.

Additional Efficacy Endpoints are:

- Experience of a loss of response after Week 12 until Week 24 (defined as a loss of at least 50% of the EASI improvement gained from Baseline to Week 12) among subjects who had an EASI 90 response at Week 12.
- Achievement of EASI score < 7 / < 3 / < 1.
- Achievement of Worst Pruritus NRS of 0 for subjects with Worst Pruritus NRS >0 at Baseline.
- Achievement of an improvement (reduction) in Patient Oriented Eczema Measure (POEM) ≥ 4 from Baseline for subjects with POEM ≥ 4 at Baseline.
- Achievement of POEM ≤ 2 / = 0 for subjects with POEM > 2 / > 0 at Baseline, respectively.
- Achievement of POEM Itch item score of 0 for subjects with POEM Itch item score >0 at Baseline.
- Achievement of POEM Sleep item score of 0 for subjects with POEM Sleep item score > 0 at Baseline.
- Change and percent change from Baseline in Patient Global Impression of Severity (PGIS).
- Achievement of "Minimal" or "Absent" on the PGIS for subjects who are "Mild" or worse on the PGIS at Baseline.
- Achievement of "Absent" on the PGIS for subjects who are "Minimal" or worse on the PGIS at Baseline.
- Change and percent change from Baseline in Patient Global Impression of Treatment (PGIT).
- Achievement of "Extremely satisfied" or "Very satisfied" on the PGIT for subjects who are "Somewhat satisfied" or worse on the PGIT at Baseline.

- Achievement of "Extremely Satisfied" on the PGIT for subjects who are "Very satisfied" or worse
 on the PGIT at Baseline.
- Achievement of an improvement (reduction) in Atopic Dermatitis Impact Scale (ADerm-IS) Sleep
 ≥ 12 from Baseline for subjects with ADerm-IS Sleep ≥ 12 at Baseline.
- Achievement of an improvement (reduction) in ADerm-IS Emotional State ≥ 11 from Baseline for subjects with ADerm-IS Emotional State ≥ 11 at Baseline.
- Achievement of an improvement (reduction) in ADerm-IS Daily Activities ≥ 14 from Baseline for subjects with ADerm-IS Daily Activities ≥ 14 at Baseline.
- Achievement of ADerm-IS Sleep ≤ 3 / = 0 for subjects with ADerm-IS Sleep > 3/> 0 at Baseline, respectively.
- Achievement of ADerm-IS Daily Activities ≤ 2 /= 0 for subjects with ADerm-IS Daily Activities
 > 2/> 0 at Baseline, respectively.

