- Achievement of ADerm-IS Emotional State ≤ 2 / = 0 for subjects with ADerm-IS Emotional State
 > 2/> 0 at Baseline, respectively.
- Achievement of an improvement (reduction) in Atopic Dermatitis Symptom Scale (ADerm-SS)
 Skin Pain ≥ 4 from Baseline for subjects with ADerm-SS Skin Pain ≥ 4 at Baseline.
- Achievement of ADerm-SS Skin Pain ≤ 1 / = 0 for subjects with ADerm-SS Skin Pain > 1/> 0 at Baseline, respectively.
- Achievement of an improvement (reduction) in ADerm-SS 7-item total symptom score (TSS-7) ≥ 28 from Baseline for subjects with ADerm-SS TSS-7 ≥ 28 at Baseline.
- Achievement of ADerm-SS TSS-7 \leq 11 / \leq 1 for subjects with ADerm-SS TSS-7 > 11 / > 1 at Baseline, respectively.
- Achievement of EASI 75 / 90, for subjects who experienced an inadequate response to previous treatment with dupilumab for AD as reported by the investigator
- Achievement of EASI 90 and a Worst Pruritus NRS of 0 or 1, for subjects with Worst Pruritus NRS
 1 at Baseline and experienced an inadequate response to previous treatment with dupilumab for AD as reported by the investigator.
- Achievement of EASI 75 / 90, for subjects who were previously treated with dupilumab for AD.
- Achievement of EASI 90 and a Worst Pruritus NRS of 0 or 1, for subjects with Worst Pruritus NRS
 > 1 at Baseline and were previously treated with dupilumab for AD.
- For subjects participating in the Wearable Tool Substudy:
 - Change from Baseline in average nightly nocturnal scratch: total scratch time and number of scratch events.
 - Change from Baseline in the following sleep parameters: total sleep time, wake after sleep onset, sleep efficiency, and sleep onset latency.

For PROs that are assessed daily (Worst Pruritus NRS, ADerm-SS, ADerm-IS), the associated endpoints will also be analyzed daily for the initial 28 days of the double-blind treatment period and the initial 28 days of the single-blind treatment period.

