# 3.3 Additional Efficacy Endpoints

All variables listed as primary or secondary endpoints will be analyzed at all applicable visits other than those listed above. In addition, the following endpoints will be evaluated at all applicable visits unless otherwise specified. Additional Efficacy Endpoints are:

- Experience of a loss of response after Week 12 until Week 24 (defined as a loss of at least 50% of the EASI improvement gained from Baseline to Week 12) among subjects who had an EASI 90 response at Week 12.
- Achievement of EASI score < 7 / < 3 / < 1.
- Achievement of Worst Pruritus NRS of 0 for subjects with Worst Pruritus NRS >0 at Baseline.
- Achievement of an improvement (reduction) in Patient Oriented Eczema
   Measure (POEM) ≥ 4 from Baseline for subjects with POEM ≥ 4 at Baseline.
- Achievement of POEM  $\leq 2$  / 0 for subjects with POEM > 2 / > 0 at Baseline, respectively.

- Achievement of POEM Itch item score of 0 for subjects with POEM Itch item score >0 at Baseline.
- Achievement of POEM Sleep item score of 0 for subjects with POEM Sleep item score > 0 at Baseline.
- Change and percent change from Baseline in Patient Global Impression of Severity (PGIS).
- Achievement of "Minimal" or "Absent" on the PGIS for subjects who are "Mild" or worse on the PGIS at Baseline.
- Achievement of "Absent" on the PGIS for subjects who are "Minimal" or worse on the PGIS at Baseline.
- Change and percent change from Baseline in Patient Global Impression of Treatment (PGIT).
- Achievement of "Extremely satisfied" or "Very satisfied" on the PGIT for subjects who are "Somewhat satisfied" or worse on the PGIT at Baseline.
- Achievement of "Extremely Satisfied" on the PGIT for subjects who are "Very satisfied" or worse on the PGIT at Baseline.
- Achievement of an improvement (reduction) in Atopic Dermatitis Impact
   Scale (ADerm-IS) Sleep ≥ 12 from Baseline for subjects with ADerm-IS Sleep
   > 12 at Baseline.
- Achievement of an improvement (reduction) in ADerm-IS Emotional State
   ≥ 11 from Baseline for subjects with ADerm-IS Emotional State ≥ 11 at
   Baseline.
- Achievement of an improvement (reduction) in ADerm-IS Daily Activities
   ≥ 14 from Baseline for subjects with ADerm-IS Daily Activities ≥ 14 at
   Baseline.
- Achievement of ADerm-IS Sleep  $\leq 3$  / 0 for subjects with ADerm-IS Sleep > 3/> 0 at Baseline, respectively.

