- Achievement of ADerm-IS Daily Activities  $\leq 2$  / 0 for subjects with ADerm-IS Daily Activities > 2/> 0 at Baseline, respectively.
- Achievement of ADerm-IS Emotional State  $\leq 2$  / 0 for subjects with ADerm-IS Emotional State  $\geq 2/> 0$  at Baseline, respectively.

[figure not shown]

- Achievement of an improvement (reduction) in Atopic Dermatitis Symptom Scale (ADerm-SS) Skin Pain ≥ 4 from Baseline for subjects with ADerm-SS Skin Pain ≥ 4 at Baseline.
- Achievement of ADerm-SS Skin Pain  $\leq 1$  / 0 for subjects with ADerm-SS Skin Pain  $\geq 1/>0$  at Baseline, respectively.
- Achievement of an improvement (reduction) in ADerm-SS 7-item total symptom score (TSS-7) ≥ 28 from Baseline for subjects with ADerm-SS TSS-7 ≥ 28 at Baseline.
- Achievement of ADerm-SS TSS- $7 \le 11 / \le 1$  for subjects with ADerm-SS TSS-7 > 11 / > 1 at Baseline, respectively.
- Achievement of EASI 75 / 90, for subjects who experienced an inadequate response to previous treatment with dupilumab for AD as reported by the investigator
- Achievement of EASI 90 and a Worst Pruritus NRS of 0 or 1, for subjects with Worst Pruritus NRS > 1 at Baseline and experienced an inadequate response to previous treatment with dupilumab for AD as reported by the investigator.
- Achievement of EASI 75 / 90, for subjects who were previously treated with dupilumab for AD.
- Achievement of EASI 90 and a Worst Pruritus NRS of 0 or 1, for subjects with Worst Pruritus NRS > 1 at Baseline and were previously treated with dupilumab for AD.
- For subjects participating in the Wearable Tool Substudy:
  - Change from Baseline in average nightly nocturnal scratch: total scratch time and number of scratch events.
  - Change from Baseline in the following sleep parameters: total sleep time, wake after sleep onset, sleep efficiency, and sleep onset latency.

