# 14.1 Changes to Planned Analyses in the Protocol

Not applicable

[figure not shown]

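### SAP 3.3 appears to use an inclusive Baseline cut-off for ADerm-IS Emotional State ≤ 2 and ADerm-SS Skin Pain ≤ 1, so a subject already exactly at target can count as an achiever; Protocol 3.4 uses the strict cut-off

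*SAP*

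**What the plan says.** Protocol 3.4 and SAP 3.3 list the same additional endpoints. Many are restricted to subjects whose Baseline score leaves room to reach the target.

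- **Emotional State ≤ 2 / 0.** Protocol 3.4 takes subjects with "ADerm-IS Emotional State > 2/> 0 at Baseline, respectively". The SAP version reads "for subjects with ADerm-IS Emotional State $\geq 2/> 0$ at Baseline, respectively".
- **Skin Pain ≤ 1 / 0.** Protocol 3.4 reads "for subjects with ADerm-SS Skin Pain > 1/> 0 at Baseline, respectively". The SAP has "ADerm-SS Skin Pain $\geq 1/>0$ at Baseline, respectively".
- **Sleep improvement of at least 12.** Protocol 3.4 reads "≥ 12 from Baseline for subjects with ADerm-IS Sleep ≥ 12 at Baseline". The SAP's Baseline condition appears as "> 12 at Baseline".

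Under SAP 9.5, categorical additional endpoints are reported as counts and percentages with 95% CIs, by visit and treatment group, as observed. SAP 14.1, on changes from the protocol's planned analyses, says "Not applicable". The version history in SAP 14.0 mentions minor changes and typo corrections but no change of endpoint definition.

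**The concern.** A Baseline restriction on a reach-the-target endpoint removes subjects who are at the target before the first dose. With a target of ≤ 2, that requires Baseline > 2. With Baseline ≥ 2, a subject at exactly 2 enters the denominator and is scored as an achiever if nothing changes. The same holds for Skin Pain at exactly 1.

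Programmers work from the SAP. If the signs are as they appear, the reported denominators would differ from the protocol's without any declaration. The endpoints concerned serve the additional objective in Protocol 3.1 on patient-reported impact of the treat-to-target approach, which names emotional health. The primary and secondary endpoints are not involved.

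**Working it through.** **Step 1. Compare the cut-offs.** The documents state no figure to reproduce here, so the check starts with the definitions.

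| Endpoint | Protocol 3.4 Baseline | SAP 3.3 Baseline | Who changes | Already at target? |
|---|---|---|---|---|
| Emotional State ≤ 2 | > 2 | ≥ 2 | SAP adds exactly 2 | Yes |
| Emotional State = 0 | > 0 | > 0 | nobody | – |
| Skin Pain ≤ 1 | > 1 | ≥ 1 | SAP adds exactly 1 | Yes |
| Skin Pain = 0 | > 0 | > 0 | nobody | – |
| Sleep improvement ≥ 12 | ≥ 12 | > 12 | SAP drops exactly 12 | No |

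Running both rules over a grid of scores in steps of 1/7 (possible 7-day averages) gives the same result: the only added values are 2.0 and 1.0, and the only lost value is 12.0.

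**Step 2. Compare with the SAP's own parallel endpoints.** In SAP 3.3 the other reach-the-target endpoints are strict and match the protocol: POEM ≤ 2 for > 2, Sleep ≤ 3 for > 3, Daily Activities ≤ 2 for > 2, TSS-7 ≤ 11 for > 11. Emotional State and Skin Pain are the exceptions. For improvement endpoints the pattern is inclusive (Emotional State ≥ 11, Daily Activities ≥ 14, Skin Pain ≥ 4, TSS-7 ≥ 28), so Sleep > 12 is the exception there. A subject at exactly 12 could meet that endpoint by reaching 0.

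**Step 3. Illustrate the size.** Three inputs are assumptions, because the documents give no Baseline distribution:

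- q: share of the SAP denominator exactly at the cut-off, 1% to 5%;
- 0.90: proportion of those subjects who stay at or below the target;
- p: achievement rate among subjects who meet the protocol's cut-off, 25% to 60%.

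Reported rate = (1 − q) × p + q × 0.90, so the shift is q × (0.90 − p).

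| p | q = 1% | q = 3% | q = 5% |
|---|---|---|---|
| 25% | +0.65 | +1.95 | +3.25 |
| 40% | +0.50 | +1.50 | +2.50 |
| 60% | +0.30 | +0.90 | +1.50 |

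(Percentage points.) For scale, take the 96 subjects that Protocol 7.6 plans as the minimum for SC1 and SC4. The standard error √(p(1 − p)/96) is 4.4 points at p = 25% and 5.0 at 40% or 60%. The shift then runs from 0.30/5.0 ≈ 0.1 to 3.25/4.4 ≈ 0.7 standard errors. The endpoint denominators may be below 96, which would make the standard errors larger.

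The result depends heavily on the inputs. With q = 10%, p = 30% and every boundary subject staying at target, the shift is 0.10 × (1.00 − 0.30) = +7.0 points. With q = 1%, p = 70% and 80% staying, it is 0.01 × (0.80 − 0.70) = +0.1.

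**The case against.** **The signs may be extraction errors.** This is the strongest objection. The two deviating signs are the only Baseline cut-offs of their kind in SAP 3.3 that the PDF conversion set as mathematical markup; the siblings that match the protocol are plain text. The same SAP text has damaged symbols elsewhere: the EASI < 21 subgroup in SAP 9.6 shows an angle bracket, the sum in SAP 9.7 has a lower limit that contradicts its own prose, and the duration formulas in SAP 6.0 have lost their minus signs. A misread cannot be excluded, which is why the fix begins with the signed document.

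The objection is not proven for these two signs. In both strings the same markup keeps a plain > before the zero, and Table D-2 in SAP Appendix D keeps > 5.0 × ULN in the same kind of markup. No other strict cut-off in the SAP's endpoint list has turned inclusive. For Sleep the objection is much stronger: horizontal strokes are lost elsewhere in this text, so a ≥ that lost its bar would look exactly like the > that appears.

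**Few subjects may be affected.** Entry requires EASI ≥ 16, vIGA-AD ≥ 3, at least 10% BSA and weekly itch ≥ 4, so very low Baseline burden should be uncommon. SAP 9.7 makes the Skin Pain Baseline a weekly average, which must equal exactly 1. This largely stands, although SAP 9.7 does not name Emotional State and the documents do not show how often either boundary value occurs.

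**Little depends on it.** The endpoints are descriptive, with no testing. That stands, and it limits the point to a minor one.

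**Conclusion.** On the text as it reads, SAP 3.3 departs from Protocol 3.4 for Emotional State ≤ 2 and Skin Pain ≤ 1, and the departure defeats the purpose of the Baseline restriction. The point is minor: it affects subjects exactly at the cut-off, in one half of each of two descriptive endpoints. A shift of about +0.3 to +3.3 points is an illustration on assumed inputs, not an estimate from the trial's documents.

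A reader might infer more than the documents support:

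- **That the added subjects cannot show a benefit.** They can, by falling to 0, and the zero half of each endpoint has the same denominator in both documents.
- **That the bias is always upward.** It is upward only while boundary subjects stay at target more often than the others reach it. With 90% staying and p = 95%, q = 5% gives 0.05 × (0.90 − 0.95) = −0.25 points.
- **That the escalated cohort, SC1, is distorted most.** The documents give no cohort-specific rates for these endpoints. SC3, the non-responders who stay on 30 mg, could equally have the lowest rate.
- **That the Sleep cut-off is a third confirmed discrepancy.** That sign is too likely to be an extraction error to be more than a query, and it would not admit anyone already at target.

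**What to change.** 1. Check the two signs in SAP 3.3 against the signed SAP. If they read > 2 and > 1, nothing needs changing.
2. If the inclusive signs stand, change the Baseline cut-offs to > 2 for Emotional State ≤ 2 and > 1 for Skin Pain ≤ 1 before database lock, and check that the programming specifications follow. Declaring the inclusive form in SAP 14.1 would make the difference visible but would still count subjects already at target.
3. In the same check, see whether the Sleep improvement cut-off should read ≥ 12 as in Protocol 3.4. If > 12 is really there, restore ≥ 12, or state and justify the difference in SAP 14.1.

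The cost is two symbols, possibly three, and a slightly smaller denominator for the Emotional State and Skin Pain endpoints. Data collection does not change.

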# 3.4 Safety Endpoint(s)

The following endpoints will be included in the safety analyses:

• Treatment emergent adverse events (TEAEs);

- Serious adverse events (SAEs);
- Adverse events of special interest (AESIs);
- Adverse events (AEs) leading to discontinuation;
- Vital signs and laboratory tests.

Laboratory assessments will include hematologic parameters, chemistry, liver function tests, and lipid parameters.

# 4.0 Analysis Populations

[figure not shown]
For simplicity, the double-blind period and the single-blind period are denoted by DB period and SB period respectively. The following population sets will be used for the analyses.

The Intent-to-Treat (ITT) Populations for the efficacy analyses are defined as:

- ITT Population of SS1 in DB Period (ITT 1 SS1 Population) includes all subjects who are randomized into SS1.
- ITT Population of SS1 in SB Period (ITT 2 SS1 Population) includes all subjects who are randomized into SS1 at Baseline and continued into SB Period.
- ITT Population of SS2 in DB Period (ITT 1 SS2 Population) includes all subjects who are randomized into SS2.
- ITT Population of SS2 in SB Period (ITT 2 SS2 Population) includes all subjects who are randomized into SS2 at Baseline and continued into SB Period.

The Safety Populations for the safety analyses are defined as:

 Safety Population of SS1 in DB Period (Safety 1 SS1 Population) consists of all subjects who are randomized into SS1 and received at least 1 dose of study drug in DB Period.

- Safety Population of SS1 in SB Period (Safety 2 SS1 Population) consists of all subjects who received at least 1 dose of study drug in SB Period of SS1.
- Safety Population of SS2 in DB Period (Safety 1 SS2 Population) consists of all subjects who are randomized into SS2 and received at least 1 dose of study drug in DB Period.
- Safety Population of SS2 in SB Period (Safety 2 SS2 Population) consists of all subjects who received at least 1 dose of study drug in SB Period of SS2.
- Safety Population for all upadacitinib treatment (ALL UPA Population) consists of all subjects who received at least 1 dose of upadacitinib in the study. This population includes two cohorts: All UPA 15 mg and All UPA 30 mg. All UPA 15 mg cohort consists of all subjects who received at least 1 dose of upadacitinib 15 mg in SS1 and SS2 (only count exposure to 15 mg). All UPA 30 mg consists of all subjects who received at least 1 dose of upadacitinib 30 mg in SS1 and SS2 (only count exposure to 30 mg). All safety analysis based on ALL UPA Population will be summarized by the above two cohorts.

These populations will be used to provide a comprehensive summary of safety based on treatment received regardless of randomization.

[figure not shown]

[figure not shown]
Table 1. Analyses Populations: ITT Populations and Safety Populations

Analyses Populations	Study Period	Analyses Groups
ITT 1 SS1	DD Dowie 4	UPA 15 mg QD
ITT 1 SS2	DB Period	UPA 30 mg QD
ITT 2 CC1		UPA 15/15 mg QD
ITT 2 SS1	CD David	UPA 15/30 mg QD
ITT 2 CC2	SB Period	UPA 30/15 mg QD
ITT 2 SS2		UPA 30/30 mg QD
Safety 1 SS1	DD D	UPA 15 mg QD
Safety 1 SS2	DB Period	UPA 30 mg QD
Cofeter 2 CC1		UPA 15/15 mg QD
Safety 2 SS1	an n i i	UPA 15/30 mg QD
S.f.4 2 SS2	SB Period	UPA 30/15 mg QD
Safety 2 SS2		UPA 30/30 mg QD
ALL LIDA	During the upadacitinib	All UPA 15 mg QD
ALL UPA	administration	All UPA 30 mg QD

# 5.0 Subject Disposition

In the DB Period, the number of subjects for each of the following categories will be summarized overall and by the two sub-studies in the ITT 1 Populations:

- Subjects randomized
- Subjects randomized and dosed in DB Period
- Subjects who completed DB Period
- Subjects who completed study drug in DB Period
- Subjects who prematurely discontinued study in DB Period
- Subjects who prematurely discontinued study drug in DB Period
- Subjects who initiated rescue medications in DB Period

The summary will be provided for SB Period for each of the following categories by the four study cohorts in the ITT 2 Populations:

- Subjects who entered SB Period
- Subjects dosed in SB Period
- Subjects who completed SB Period
- Subjects who completed study drug in SB Period
- Subjects who prematurely discontinued study in SB Period
- Subjects who prematurely discontinued study drug in SB Period
- Subjects who initiated the rescue medications in SB Period

# 6.0 Study Treatment Duration and Compliance

For the DB Period and the SB Period, the duration of treatment will be summarized by sub-studies and treatment groups using Safety 1 and Safety 2 Populations, respectively.

[figure not shown]
#### **DB** Period:

- For subjects who did not continue into SB Period:
  - Date of last dose of study drug in DB Period Date of first dose of study drug in DB Period + 1.
- For subjects who continued into SB Period:
  - Minimum of (Date of first dose of study drug in SB Period Date of first dose of study drug in DB Period, Date of last dose of study drug in DB Period Date of first dose of study drug in DB Period + 1.)

#### **SB Period:**

For subjects who continued into SB Period:

• Date of last dose of study drug in SB Period Date of first dose of study drug in SB Period + 1.

#### **ALL UPA:**

Study drug duration during the administration of study drug in ALL UPA Population is defined as follows.

For All UPA 15mg cohort:

• Date of last dose of upadacitinib 15mg Date of first dose of upadacitinib 15 mg + 1.

For All UPA 30mg cohort:

• Date of last dose of upadacitinib 30mg Date of first dose of upadacitinib 30 mg + 1.

Duration of treatment will be summarized using the number of subjects treated, mean, standard deviation, median, minimum and maximum. In addition, the number and percentage of subjects in each treatment duration intervals ( $\geq 4$  weeks,  $\geq 12$  weeks,  $\geq 16$  weeks, and achieving 24 weeks) will be summarized for Safety 1, Safety 2, and All UPA Populations.

Treatment compliance for DB Period and SB Period will be summarized by treatment groups for Safety 1, and Safety 2 Populations. Treatment compliance is defined as the number of tablets actually taken divided by the number of tablets that should have been taken. For subjects who prematurely discontinued the study drug, the planned tablets will only be counted prior to that scheduled visit of discontinuation. Percent compliance will be summarized.

# 7.0 Subject Characteristics

# 7.1 Demographics and Baseline Characteristics

[figure not shown]
The following demographic and baseline characteristics will be summarized for each treatment in each ITT 1 Population.

#### **Demographics:**

- Sex (female, male)
- Age (years)
- Age categories (18 to < 40;  $\ge 40$  to < 65 years).
- Race (White, Black or African American, Asian, American Indian/Alaska Native, Native Hawaiian or Other Pacific Islander)
- Ethnicity (Hispanic or Latino, Not Hispanic or Latino)
- Body Weight (kg)
- Tobacco/Nicotine and Alcohol Use:
  - Tobacco/Nicotine Use (unknown, never, current, former)
  - Alcohol Use (unknown, never, current, former)

### **Baseline Characteristics**

- Baseline EASI (< median; ≥median)
- Baseline EASI (<21;  $\ge 21$ )
- EASI overall score and body region scores
- Body Surface Area (BSA)
- Baseline vIGA-AD (3, 4)
- Previous systemic therapy for AD (with and without)
- Prior Atopic Dermatitis Treatment
- Worst Pruritus NRS (Weekly Average)
- DLQI, POEM, PGIS, PGIT
- ADerm-IS sleep domain, daily activity domain, and emotional state domain
- ADerm-SS Skin pain and TSS-7
- Prior use of dupilumab
- Disease duration since diagnosis (years)
- Disease duration since symptoms started (years)
- Duration between symptoms and diagnosis (years)

